Heinrich's Quality of Life Scale-Client Version - Is a 21 item semi-structured interview based rating of individual's psycho-social functioning and satisfaction with various life domains.

Temple University Community Participation Scale - is a 26 item instrument measuring frequency of participation and importance of various community activities (e.g., movies, library). Test-retest reliability is .7 and internal consistency is .9.

Scales of Psychological Well-Being - is a 54-item measure rating wellbeing (from strongly disagree to strongly agree) including subscales of mastery, personal growth, purpose in life, self-acceptance, autonomy and positive relations with others. Internal consistency is .94. It has been successfully used with individuals with SMI.

Maryland Assessment of Recovery - is a 25-item scale that assesses a person's sense of recovery from mental illness across a variety of dimensions. Internal consistency is .95 and test-retest reliability is .89).

Personal Growth and Recovery Scale - (BU CPR, 2009) - is a 16-item, 4 point scale (strongly disagree to strongly agree) developed for previous Photovoice study. Items tap aspects of person's psychosocial functioning and recovery. Internal consistency is 0.94 and retest reliability is .79.

Photovoice Program Fidelity Scale - the Photovoice Fidelity Scale was developed and used in our pilot RCT study (Russinova et al., 2014). The scale includes content fidelity items specific to each of the 10 Photovoice sessions and 13 process fidelity items which are specific to the Photovoice program as a whole. All items are measured on a 4-point scale from 1, "strongly disagree" to 4, "strongly agree". All Photovoice sessions will be audiotaped and fidelity will be assessed based on review of all audio-recorded sessions.

We will use a **Demographic Questionnaire** developed by the Boston University Center for Psychiatric Rehabilitation and previously used in multiple research studies. Questions inquire about the person's demographic characteristics, such as age, race, gender, education, employment status, housing situation, and basic clinical characteristics, such as perceived physical health and use of different mental health services in the past 3 months. We are using an abbreviated version of this questionnaire at post-treatment and follow-up assessments to capture information only on time varying variables included in the questionnaire.

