We will employ several strategies to retain participants in both the VEP sessions and in study assessments. First, we will use information from the Locator Form they will complete at baseline. We may also gather contact information from the participant's Riverside treatment team. Participants in the experimental arm will receive regular calls from the Photovoice peer leaders to encourage participation in classes. We have established a protocol for the peer leaders to call all participants the day before each Photovoice class. If they do not reach the participant, they leave a voice message. For participants who have expressed a preference for email reminders, peer leaders will send an email message the day before each class. If participants miss a class they will be encouraged to continue their involvement. Calls from the Photovoice peer co-leaders will allow an opportunity to discuss with participants any barriers to participation, such as transportation issues and to take steps to remedy those barriers.

We will implement the following protocol for contacting participants in both the experimental and control condition about upcoming assessments. The Clinical

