Photovoice peer leaders who encounter any similar reports of suicidal thoughts or intentions before, during, or after a Photovoice class will be taught how to follow up the statement by asking similar questions to those described above for the interviewer (in private, if the statement was made during a class), and will follow up by contacting immediately Riverside clinical staff using the same procedures described above for interviewers if significant suicide risk is identified in a participant. We will work with Riverside staff to establish a protocol of which clinical staff should be contacted to prevent any harm if significant suicide risk is identified in a participant. Study participants will be informed as part of the consenting process and at the beginning of each assessment that if they were to share any risk of harm to themselves or others, such information will not be kept confidential and clinical staff at the agency will be informed and will follow the procedures of the agency to ensure participants' safety.

10. Care and Treatment Statement

Participation in the study will not result in any change to the services outside of the study that participants are already receiving or plan to enroll in.

11. Informed Consent (See Part F)

Consent will be obtained in person in an individual meeting with the Project Coordinator. The details of the study contained in the informed consent form will be reviewed section by section. After each section of the consent, the Project Coordinator will ask if potential participants have any questions about that section of the consent form. Individuals will be requested to complete the quiz (see attached) to determine their capacity to consent before proceeding with obtaining their signature on the consent. The quiz responses will be reviewed discreetly to ensure that each individual gets 8 out of the 10 items correct. If an individual does not get the required number of answers correct, the Project Coordinator will review the incorrect answers with the individual and make an individual determination of the individuals' capacity to understand the details of the study and to give knowing consent. If the person is found to be capable of giving consent, the potential participant will be asked to sign the consent form. If the potential participant

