We will take several steps to insure that staff follows procedures to maintain privacy and confidentiality. First, all new staff will be required to be oriented and trained in procedures to maintain confidentiality of information, including written and electronic materials. Staff is required to sign a Confidentiality Contract, which describes the serious nature of maintaining confidentiality and enumerates procedures for maintaining it. All project staff will be required to take and pass the CITI training course on the protection of human subjects. In addition, project staff will be instructed about PHI, the need to identify individuals by arbitrary identification numbers, the need to file materials with names or key lists separate from research materials, electronic privacy, the need for non-identifiable correspondence materials from the Center, removing or blacking out participant names from any forms; sorting all data in locked file cabinets; securing all computers that store data; and destroying audiotapes used for interviewer reliability checks and fidelity ratings at the end of the project.

16. Final Product(s)

Final results will be reported in aggregate form only. Results may be prepared for publication in peer reviewed professional journals in mental health and rehabilitation, and used as preliminary data for future development of the intervention.

17. Financial Summary

The project is being funded by the National Institute of Mental Health - Grant Proposal MH102230-01A1.

18. Compensation for Injuries

We do not anticipate any injuries related to participation in the study and do not plan on any compensation for injury. There may be a minimal risk for physical injuries while individuals are taking pictures in the community. The Informed Consent Form informs participants that if this occurs, the cost of required medical services will have to be covered by their insurance or by them personally.

19. Insurance

There are no entitlements or insurance for the subject that will be purchased or invoked for this project. There is no other insurance purchased by Boston University for the subjects.

20. Use of DMH Resources

No DMH resources will be used for this study.

21. Other IRBs Involved

Boston University Charles River Campus (CRC) IRB.

22. Adverse Events

An adverse event for this study is consonant with the guidelines set forth by the MA DMH. Reporting guidelines will be followed in the event of an adverse event.

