It is highly unlikely that we will experience a serious, unexpected adverse events related to study participation in the Photovoice intervention. Riverside staff will be asked to report any unexpected serious adverse event among study participants to the PI within 3 days of becoming aware of the occurrence of any such event. The Project Coordinator will be required to report such events to the PI within 24 hours of becoming aware of their occurrence. The PI will follow the requirements of the Data Safety and Monitoring Board and the MA DMH IRB (the IRB of record for the study): a) in case of a serious adverse event – verbal notification as soon as possible and in writing by the next business day following the event; and b) non-serious adverse event will be monitored, recorded, and reported to the IRB Chair every 4 months. The PI will notify NIMH within 7 days of becoming aware of the occurrence of a study-related serious adverse event and will report non-serious adverse events in the corresponding progress reports to NIMH.

Continuous and close monitoring of study participants' safety by the PI will occur in conjunction with the Dartmouth College Data Safety Monitoring Board (DSMB). The current research project is a Phase II trial, involves a low risk intervention, is not conducted with a vulnerable population, and is not blinded to participant or treatment provider. However, given that the research is being conducted in three locations within one agency, a Data Safety and Monitoring Board (DSMB) will be constituted to provide additional human subjects' oversight. Two Investigators on this project are faculty at Dartmouth Medical School: Drs. [name] and [name] (statistician). Through this affiliation with Dartmouth, we plan to use their standing DSMB comprised of three psychiatrists and a psychologist (see attached bio sketches of the Dartmouth Medical School DSMB members). [name] has used the Dartmouth DSMB for multiple prior RCTs, supported by NIMH, evaluating the impact of psychosocial interventions on persons with SMI. The DSMB will establish a risk level for the study, and based on that assessment

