will determine the frequency of DSMB meetings and review of pertinent data. The DSMB Chair ([name]) will be notified by the PI of serious adverse events that are study related using the protocol specified in the next paragraph. An ongoing record of all adverse events will be kept by the PI for use and review of the DSMB at the meetings. Minutes will be kept of DSMB meetings, including any discussion or decisions made about adverse events, and including those that could affect the conduct of the study. The DSMB will report back to the PI within one business day any implications for patient safety that arise from discussions during the scheduled DSMB meetings.

23. Required Attachments

Resume of the Principal Investigator
Certificate of Completion of the Human Subjects Training Course
Unaffiliated Investigator Agreement
Recruitment Flyer and
Consent to Contact Form
Informed Consent Form
Copies of the research instruments
Competency quiz

24. Attachments that are appropriate, when applicable:

- (a) Approval Form(s) from other IRBs that have reviewed this project.
- (b) Copies of non-standardized questionnaires, instruments, tests, etc.
- (c) Copies of posters, flyers, letters, etc.
- (d) Scripts of intended communications by telephone or interview.
- (e) External research protocols (usually, only five (5) copies are required of the technical drug research protocols - check with the CORRC before submitting materials).

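### The protocol describes no systematic, arm-neutral way of eliciting adverse events for the DSMB's record, and the much heavier study contact in the Photovoice arm creates a risk of uneven ascertainment

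*Protocol*

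**What the plan says.** **How events enter the record.** Section 22 states that "An ongoing record of all adverse events will be kept by the PI for use and review of the DSMB at the meetings". For serious events, "Riverside staff will be asked to report any unexpected serious adverse event among study participants to the PI within 3 days", and "The Project Coordinator will be required to report such events to the PI within 24 hours of becoming aware of their occurrence". For the rest, a "non-serious adverse event will be monitored, recorded, and reported to the IRB Chair every 4 months"; no source, form, visit or question is named. The definition is by reference: "An adverse event for this study is consonant with the guidelines set forth by the MA DMH". The data management text in section 7 provides a Microsoft Access database that covers adverse events, among other things, but does not say what feeds it.

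**What the interviews collect.** Both arms have the same four interviews (baseline, post-treatment, 3 and 6 months) with a blinded Clinical Interviewer. No instrument listed in section 7 is described as an adverse event inquiry. Some safety-relevant information is gathered. The battery includes a symptom scale. The Demographic Questionnaire asks about "use of different mental health services in the past 3 months", and a shortened form with the time-varying items is repeated at follow-up. Under section 9, suicidal statements at interview trigger set probes, and a positive score leads to contact with Riverside clinical staff. Nothing says that any of this reaches the PI's record.

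**Contact by arm.** Photovoice has 10 sessions in 10 weeks; the control condition has one 60-minute session. For Photovoice only, "We have established a protocol for the peer leaders to call all participants the day before each Photovoice class". Section 9 gives a further duty to "Photovoice peer leaders who encounter any similar reports of suicidal thoughts or intentions before, during, or after a Photovoice class": they ask follow-up questions and contact Riverside clinical staff if the risk is significant. Section 8 sends class distress that the co-leaders cannot settle to clubhouse staff and, if needed, to the clinician or case worker.

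**The concern.** A record built on spontaneous reports depends on how often somebody is in a position to notice. Here that differs by arm by design. The only study contacts that are identical in both arms, the interviews, have no stated link to the record.

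There is also an indirect path from classes to the record. Distress and suicidal statements that come up around Photovoice classes are passed to Riverside staff, and Riverside staff are the people asked to report to the PI. Section 8 adds that some co-leaders are themselves Riverside peer specialists. All Photovoice sessions are audiotaped and reviewed for fidelity; no such review is described for the control session.

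At stake is the DSMB's ability to read its own data. An excess of events under Photovoice could reflect harm or only more frequent contact, and the record as described could not separate the two. Section 18 (Compensation for Injuries) names one risk particular to the intervention, injury while taking pictures in the community, yet no listed assessment asks about injury.

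**Working it through.** The documents give no adverse event rate or detection rate, so there is no figure of the plan's own to reproduce. The check has two parts.

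**1. Scheduled study contacts after randomization** (section 7)

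- Photovoice: 10 sessions + 3 interviews = 13; with up to 10 day-before calls, 23.
- Control: 1 session + 3 interviews = 4.
- Ratio: 13/4 = 3.25 without calls, 23/4 = 5.75 with them.

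The calls are a maximum, because some will be voicemails or be replaced by emails.

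**2. What unequal contact could do to the record when true risk is equal**

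Let b be the probability that an event reaches the record by the passive staff route, taken as equal in both arms. Let q be the added probability per group session, and k the number of sessions (10 or 1). Then

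P(recorded) = 1 − (1 − b)(1 − q)^k.

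Both b and q are assumptions. Reminder calls are left out.

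Example, b = 0.6 and q = 0.10:

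- Photovoice: 1 − 0.4 × 0.9^10 = 1 − 0.4 × 0.349 = 0.86.
- Control: 1 − 0.4 × 0.9 = 0.64.
- Ratio: 0.86/0.64 = 1.34.

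With 96 per arm and an assumed true event proportion of 20% (19.2 events per arm), the record would show about 16.5 against 12.3 events.

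Ratio of recorded events, Photovoice to control:

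| | q = 0 | q = 0.05 | q = 0.10 | q = 0.20 |
|---|---|---|---|---|
| b = 0.3 | 1.00 | 1.73 | 2.04 | 2.10 |
| b = 0.6 | 1.00 | 1.23 | 1.34 | 1.41 |
| b = 0.9 | 1.00 | 1.04 | 1.06 | 1.08 |

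Two limits apply. The model lets every session be an occasion to notice the event, which suits an event present from the start. An event arising after the classes end has k = 0 in both arms and a ratio of 1.00, so the imbalance concerns the 10-week treatment period rather than the whole of the roughly 34 weeks. In the other direction, the ratio rises further if b is below 0.3. This is possible for non-serious events, for which no source is named. The value 2.10 is the top of the range examined, not a bound.

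**The case against.** The strongest reply is that the stated route for serious events makes no distinction by arm. Every participant must be receiving Riverside services, and Riverside staff report on all of them on the same terms. Peer leaders are told to contact clinical staff, not the PI. The SAP text has no between-arm comparison of events, no stopping rule on event counts appears, and the intervention is low risk.

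Much of this stands. A reader might infer from the contact counts that the record is in fact uneven. The documents do not support that: the common staff route could detect nearly everything, and session findings might add nothing. What does not stand is the claim that nothing carries class observations towards the record. Sections 8 and 9 send them to Riverside staff, and section 22 asks Riverside staff to report. Their stated duty covers unexpected serious events only. For non-serious events and distress the record depends on who happens to hear of them.

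A reader might also infer that nothing could be detected once the classes end. That goes too far. The 3- and 6-month interviews include suicide probes when prompted, symptom ratings and, presumably, service use, and administrative service data are collected after the 6-month interview. The gap is the missing link from these to the record.

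Finally, the MA DMH guidelines and the attached instruments are not visible here. An inquiry there cannot be excluded.

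**Conclusion.** The point holds as a gap in method and a risk of bias, not as a demonstrated imbalance. The protocol describes no systematic elicitation of adverse events that is the same in both arms and feeds the DSMB's record. Given 23 (or 13) scheduled contacts against 4, uneven ascertainment is credible, mainly for non-serious events and distress during the treatment period.

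Its size cannot be fixed from the documents. With equal true risk the recorded ratio is 1.00 if sessions add nothing, 1.04 to 1.08 if the passive route catches 90% of events, and up to about 2.1 if it catches 30%. These figures rest on assumed detection rates and on independent chances of detection at each session. The remedy is cheap enough that the sponsor should make the change without needing to know where in that range the trial lies.

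**What to change.** - At the end of the post-treatment, 3-month and 6-month interviews in both arms, after all outcome measures, the Clinical Interviewer asks the same short yes/no questions: hospitalization, emergency visit, self-harm and injury since the last interview. The interviewer does not ask about circumstances and reminds participants not to mention their group. This order matters, because an account of an injury while taking pictures would reveal allocation to the blinded interviewer.
- The Project Coordinator, who already knows allocation, collects the details on a fixed form and logs them in the Access adverse event database.
- The same log receives hospitalizations from the service-use items and positive suicide probes. Existing clinical responses to those findings are untouched.
- Record the source of each event. Show the DSMB interview-elicited events by arm, separately from spontaneous reports.
- If the MA DMH guidelines or the attached instruments already contain such an inquiry, cite it in section 22 and state that its answers enter the record.

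The cost is one form and a few minutes in an interview that section 13 puts at about two and a half hours, with no new visits. More events will be logged, and a small risk of unblinding the interviewer for later assessments remains.

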Testing Effectiveness of a Peer-Led Intervention to Enhance Community Integration

NCT02508480

Statistical Analysis Plan

Date: July 24th, 2019

Statistical Analysis Plan-

Intent-to-treat analyses will be conducted on the full sample of participants, regardless of actual exposure to the Photovoice program. Based on our pilot RCT study of Photovoice we are confident that majority of participants randomized to the Photovoice group will receive the intervention. However, if significant rates of non-exposure occur, we will also conduct separate analyses on treatment exposed participants. The intent-to-treat sample will include all participants for whom we have baseline data. It assumes that participants who are not exposed to the Photovoice program are not also study dropouts, and thus the analyses will include all available study participants. These analyses are the primary gauge of the effectiveness of the Photovoice program. If dropout rates from the Photovoice group exceed 20% we will explore the question of treatment effectiveness for those who participated in the Photovoice program. Participants will be classified based on their level of participation, with "exposure" defined as attendance at more than one-half of the 10 sessions (6 or more), with parallel analyses comparing the exposed Photovoice group with SAU. We will test the following primary hypotheses:

Hypothesis 1: Compared to SAU, clients randomized to the Photovoice program will demonstrate significantly greater improvements at post-treatment and 3- and 6-month follow-ups in their capacity to resist public prejudice and discrimination, including reduced self-stigma and perceived stigma, and increased proactive coping with public prejudice and discrimination (e.g., confronting prejudicial and discriminatory attitudes and behaviors). We will test this hypothesis by using the total score on the Internalized Stigma of Mental Illness Scale⁷⁸ and on the Stigma Scale⁹³, and the sum of the two proactive coping subscales on the Coping with Stigma Scale (Educating Others, Challenging Others)⁹² and fitting covariance pattern models (using SAS PROC MIXED) and examining time (baseline, post-treatment, 3- and 6 month follow-ups), group, and the group by time interaction effects.

Hypothesis 2: Compared to SAU, clients randomized to Photovoice will show significantly greater improvements at post-treatment and 3- and 6- month follow-ups in community functioning and integration. The scores on the Temple University Community Participation Scale will be used as measures of community integration.

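### If triggered, the exploratory exposure analysis compares Photovoice attenders with all of SAU; this is not a randomized comparison, and no randomization-based estimate of the effect in attenders is planned (low severity; ITT unaffected)

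*SAP*

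**What the plan says.** The opening paragraph of the SAP plans ITT analyses of everyone with baseline data, whatever their attendance, and says of them: "These analyses are the primary gauge of the effectiveness of the Photovoice program". It adds an exposure analysis under two conditions. The first is that "if significant rates of non-exposure occur, we will also conduct separate analyses on treatment exposed participants". The second reads: "If dropout rates from the Photovoice group exceed 20% we will explore the question of treatment effectiveness for those who participated". Exposure means more than half of the 10 sessions, that is 6 or more. The method is given in one clause: "with parallel analyses comparing the exposed Photovoice group with SAU". SAU is not restricted in any way, and no adjustment, complier-effect or instrumental-variable method is named.

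Hypothesis 1 concerns change: Photovoice participants "will demonstrate significantly greater improvements at post-treatment and 3- and 6-month follow-ups". The model examines time, "group, and the group by time interaction effects".

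Three points in the protocol bear on this. The recruitment text before Section 7 plans 96 participants per group, and tells only those randomized to control the date of a 60-minute peer-led session on coping with prejudice. Section 7 invites control participants into Photovoice only after their 6-month assessment. Section 7 also has the peer leaders call Photovoice participants before each class.

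**The concern.** The 6-session rule can be applied only to the Photovoice arm, because SAU has a single session. Applying it removes low attenders from one arm and leaves the people like them in the other. If regular attenders would have changed differently over time without the program, that difference enters the exposed-versus-SAU contrast and looks like a program effect, or hides one.

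What is at stake is limited. Once triggered, this is the plan's only analysis aimed at those who took part, and the SAP attaches no caution on how to read it. ITT answers a different question, the effect of being assigned to Photovoice.

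**Working it through.** **Inputs.** From the documents: 96 per arm; exposure at 6 or more sessions; a 20% threshold, used here as the lower non-exposed share. Assumed, because the documents give no values: non-exposed share q of 0.20 or 0.40; gap d in untreated change (attenders minus others, in SD of the outcome) of 0.1 to 0.3; correlation between visits ρ of 0.5 or 0.7. The plan states no figure for this analysis, so there is none to reproduce.

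**Bias.** Let attenders' mean untreated change be A and the others' be A − d. The exposed group averages A. SAU averages (1 − q)A + q(A − d) = A − qd. With no program effect the contrast is therefore qd; with an effect τ in attenders it is τ + qd.

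**Rejection rate, single change contrast, two-sided 5%.** SE = √[2(1 − ρ)/(96(1 − q)) + (2(1 − ρ) + q(1 − q)d²)/96]. Example with q = 0.20, d = 0.3, ρ = 0.5: √[1/76.8 + 1.0144/96] = 0.154. The bias is 0.06, the ratio 0.39, and the rejection rate 6.8%.

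| q | d (SD) | Bias qd (SD) | Rejection, ρ 0.5 / 0.7 | 3-df group by time, simulated, ρ 0.5 / 0.7 |
|---|---|---|---|---|
| 0.20 | 0.1 | 0.02 | 5.2 / 5.3% | 5.8 / 5.3% |
| 0.20 | 0.2 | 0.04 | 5.8 / 6.3% | 6.2 / 6.7% |
| 0.20 | 0.3 | 0.06 | 6.8 / 7.9% | 6.3 / 7.6% |
| 0.40 | 0.1 | 0.04 | 5.7 / 6.1% | 5.6 / 5.5% |
| 0.40 | 0.2 | 0.08 | 7.7 / 9.5% | 7.0 / 8.4% |
| 0.40 | 0.3 | 0.12 | 11.1 / 15.2% | 9.1 / 12.8% |

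The last column uses 3,000 runs per setting, four visits and compound symmetry. With no gap the same simulation rejected 4.6-5.5%.

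**Direction.** A negative gap reverses the sign. With τ = 0.30 and d = −0.3 the contrast is 0.30 − 0.06 = 0.24 at q = 0.20, and 0.30 − 0.12 = 0.18 at q = 0.40.

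**Complier estimate.** SAU cannot join Photovoice before the 6-month assessment, so non-compliance is one-sided and the estimate is the ITT contrast divided by (1 − q). If assignment changes outcomes by h in the non-exposed, it becomes τ + qh/(1 − q). With τ = 0.30:
- h = +0.15 (few sessions or calls give half the effect): 0.30 + 0.25 × 0.15 = 0.34 at q = 0.20, and 0.30 + 0.667 × 0.15 = 0.40 at q = 0.40.
- h = −0.15 (same size, opposite sign, as if missing the control session cost that much): 0.26 and 0.20.

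**Precision, baseline-adjusted.** Exposed versus SAU: SE = √[(1 − ρ²)(1/(96(1 − q)) + 1/96)]. Complier: SE ≈ √[2(1 − ρ²)/96]/(1 − q). Root mean squared error (RMSE) at d = 0.3, with the exclusion restriction holding (h = 0), is:

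| q | ρ | SE exposed vs SAU | SE complier | RMSE exposed vs SAU | RMSE complier |
|---|---|---|---|---|---|
| 0.20 | 0.5 | 0.133 | 0.156 | √(0.133² + 0.06²) = 0.146 | 0.156 |
| 0.20 | 0.7 | 0.109 | 0.129 | 0.124 | 0.129 |
| 0.40 | 0.5 | 0.144 | 0.208 | √(0.144² + 0.12²) = 0.187 | 0.208 |
| 0.40 | 0.7 | 0.119 | 0.172 | 0.169 | 0.172 |

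At d = 0.5, q = 0.20 and ρ = 0.5 the order turns: 0.166 against 0.156.

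**The case against.** The strongest reply is that the trial's conclusion does not rest on this analysis. It is conditional, worded as exploration, and subordinate to an ITT analysis that keeps randomization intact. Near 20% non-exposure, gaps up to 0.3 SD move the rejection rate little. The complier estimate has no lower mean squared error at such gaps, relies on an untestable assumption, and has a p-value close to that of ITT. A reader given the ITT result and the attendance counts could do the division unaided. All of this stands. It makes the point a low-severity one and rules out substituting one analysis for the other.

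It does not remove the point. The planned comparison is not randomized, the SAP does not say so, and the label costs nothing.

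A reader might infer three stronger things. The first is that the plan has no randomization-based estimate at all. It has one, the primary ITT analysis; only an estimate of the effect in attenders is missing. The second is that the comparison favours Photovoice. The documents give no attender gap, so neither sign nor size is known. The third is that any difference between attenders and others inflates the result. A stable difference in level does not affect the group-by-time term, which tests greater improvement; it would distort the group main effect.

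**Conclusion.** The point holds at low severity. Exposed versus SAU selects one arm on behaviour after randomization, and no randomization-based estimate of the effect in attenders accompanies it. With no program effect, the bias is 0.02-0.06 SD with 5.2-7.9% rejection at 20% non-exposed, and 0.04-0.12 SD with 5.7-15.2% at 40%, for assumed gaps of 0.1-0.3 SD in untreated change and visit correlations of 0.5-0.7. Only the 96 per arm comes from the documents; the size in this trial depends on attendance and on a gap that they do not report. ITT is unaffected.

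**What to change.** 1. Label exposed versus SAU as descriptive and non-randomized, and base any statement from it on the group-by-time term, not the group main effect.
2. Beside it, report a supportive complier average causal effect on all randomized participants, with arm as instrument and 6 or more sessions as exposure. The simplest form is the PROC MIXED ITT change contrast at each follow-up divided by the share of the Photovoice arm exposed, with an interval. If its assumption holds, the difference between the two estimates indicates the selection term qd.
3. State the exclusion restriction and that it can fail in both directions. The estimate is too large if 1-5 sessions or the peer-leader calls help. It is too small if the 60-minute session helps, because it is scheduled only for the control arm and Photovoice non-attenders do not get it.
4. Note that the ratio inherits the missing-data assumptions of the ITT model. The SAP's statement about non-exposure and dropout, "It assumes that participants who are not exposed to the Photovoice program are not also study dropouts", is an assumption to check against the data.

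The cost is a short SAP paragraph, since session counts are already needed. The downsides are a wider interval (SE about 0.13-0.21 SD against 0.11-0.14 SD), a p-value close to ITT, and no gain in mean squared error when the gap is about 0.3 SD or less. Both estimates should therefore be shown.
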